2.4.4 Minimization of Bias

There will be no specific sex, ethnic or racial background for enrollment. Placebo arm is introduced to increase the ability to differentiate between the pharmacologic effects of pregabalin and

other possible effects. The study is designed as a cross-over in order to minimize inter-subject variability. The investigators and the subjects will be blinded to treatment allocation sequence.

2.4.5 Observations and Measurements

2.4.5.1 Primary Outcome Measures

Primary outcome:

Correlation between MPT at baseline and reduction in spontaneous pain intensity (% reduction on 0-10 NRS) at the end of 4-week treatment. The slopes of the correlation obtained from pregabalin vs. placebo will be compared.

2.4.5.2 Secondary Outcome Measures

Secondary outcomes:

- 1). Absolute change in pain intensity from baseline to 4 weeks with pregabalin vs. placebo, and from that data – the proportion of patients achieving 50% or more reduction in pain intensity.
- 2). Change from baseline to week 4 of the following items assessed by questionnaires: NPSI, BPI, DAPOS, and SPI.
- 3). Exploratory analysis to investigate potential correlation between various QST variables (WDT, CDT, HPT, CPT, WSI, TS, CPM) and pain reduction with pregabalin vs placebo.
- 4) Exploratory analyses to investigate potential correlation between skin biopsy parameters (IENFD, NFLD) and pain reduction with pregabalin vs. placebo.

2.4.6 QST protocol

Quantitative sensory testing will be performed on the dorsal mid-foot. If asymmetry in pain intensity exists between extremities, QST will be performed in the more painful foot; otherwise the foot will be chosen randomly. The ipsilateral shoulder will serve as control area.

A description of the QST procedures follows:

Determination of mechanical pain threshold (MPT)

Equipment: A set of standardized weighted metal probes (Nervetest, MRC systems) exerting pressure of 8, 16, 32, 64, 128, 256 and 512 mN.

Methods and Background:

The standardized metal probes will be used in a modified method of levels manner, 3 series of increasing stimulus intensities to detect the mechanical pain threshold. Beginning with an applied force of 8mN, stimuli increase in intensity until the sensation induced by increased pressure can be described as 'painful'. The corresponding force is used to represent the first MPT value. The procedure is then repeated a total of 3 times and until a total of 3 values are obtained, from which the mean MPT is determined.

Thermal detection and thermal pain thresholds

Equipment: The Thermal Sensory Analyzer (TSA-II platform - Medoc, Ramat Yishai, Israel) will be used to determine thermal detection and pain thresholds. This equipment is used globally for functional assessment of pain and temperature-conducting nerve fibers (C and A-delta fibers).

Method and Background: Using the thermal sensory analyzer, cold and warm detection thresholds

(CDT and WDT, respectively), as well as cold and heat pain thresholds (CPT and HPT, respectively) will be determined (Fruhstorfer, Lindblom et al. 1976, Yarnitsky, Sprecher et al. 1995). The thermode with contact area of 9.0 cm² is applied to the tested site, and all thresholds are determined by continuous ramping of temperature from 32°C baseline temperature by 1°C/s until the subject presses the ‘stop’ button. Cut-off temperatures are 0°C and 50°C, to minimize thermal damage to the skin. The baseline temperature to which the thermode returns before each test is 32°C. The average threshold is calculated from three measurements in each area. The warm sensibility index (WSI) will be calculated by the following formula:

$$WSI = \frac{HPT\ (^{\circ}C) - WDT\ (^{\circ}C)}{HPT\ (^{\circ}C) - \text{baseline temp. (32}^{\circ}\text{C)}}$$

Determination of mechanical detection threshold (MDT)

Equipment: A set of standardised von Frey filaments (0.25, 0.5, 1, 2, 4, 8, 16, 32, 64, 128 and 256mN). The contact area of the hairs with the skin is of uniform size (<1 mm²) and texture.

Methods and Background: Standardised von Frey filaments will be used in a modified “method of limits” manner using 3 series of increasing and decreasing stimulus intensities to determine the geometric average as the tactile detection threshold of the affected and unaffected skin areas (Baumgartner, Magerl et al. 2002).

Von Frey filaments of different stimulus intensities are used to determine the tactile detection thresholds. A filament eliciting 16mN force* is applied first, followed by filaments of consecutively lower intensity until the patient cannot detect the stimulus being applied. This respective force represents the first threshold value. The order in which the stimuli are applied is then reversed and stimuli of consecutively greater intensity are applied until sensation is detected (this intensity becomes the second value). Again filaments with decreasing intensity are applied until in total 3 upper and lower values of detection are fulfilled from which the mechanical detection threshold can be determined.

* In case the first von Frey filament with an intensity of 16mN is not detected, the next highest intensity filament which can be detected must be used as a starting intensity. However, the relevant force of this stimulus is not documented. Filaments with consecutively lower intensity are applied until the patient cannot detect the stimulus being applied. The procedure is followed as above; until in total 3 upper and lower values of detection are fulfilled from which the mechanical detection threshold can be determined.

Determination of wind-up ratio (WUR)

Equipment: A standardized weighted metal probes (Nervetest, MRC systems) exerting pressure of 256mN.

Methods and Background: In this test a pinprick (256mN) is first applied singularly. After that a series of 10 identical pinprick stimuli are applied with a frequency of 1 s⁻¹ within an area of 1 cm². Immediately following the single stimulus and series of stimuli, an evaluation of the sensation must be provided according to NRS (0-10, ‘0’: ‘no pain’, ‘10’: ‘worst pain imaginable’). A ratio is calculated using these values. This procedure will be repeated 3 times. A geometric average of the ‘wind-up’ is calculated from the two ratios (Price, Hu et al. 1977, Magerl, Wilk et al. 1998).

Determination of conditioned pain modulation (CPM) efficiency

[figure not shown]
Equipment: The Q-Sense Thermal Analyzer (Medoc, Ramat Yishai, Israel) will be used for CPM paradigm testing.

Methods and Background

The Q-Sense works on the same principle as TSA-II, which is used for determining the thermal thresholds. However, Q-Sense is equipped with two 3x3cm Peltier thermodes – one used as conditioning stimulus, and the other used as test stimulus. The intensity of the conditioning stimulus will be determined individually by temperature that elicits pain intensity of 30 on 0-100 NRS. The intensity of test stimulus will also be determined individually, at the temperature that elicits pain intensity of 60 on 0-100 NRS.

The conditioning stimulus will be applied at left shoulder, while the test stimulus will be applied at the right shoulder. The length of the conditioning stimulus is 60 seconds, during the last 30 seconds of which the pain stimulus is applied. The stimuli are applied according to the diagram in Fig.2 below – and the difference between the intensity of pain stimulus without conditioning and between the intensity of pain stimulus with concomitant conditioning is the CPM magnitude. CPM>0 implies efficient descending pain modulation.

Figure 2. CPM paradigm testing.

2.4.7 Statistical Methods

The primary outcome is the comparison of slopes of the two correlations: baseline MPT vs % pain reduction with pregabalin, and baseline MPT vs % pain reduction with placebo. Percent pain reduction will be assessed from the difference in average pain intensity at baseline and the average daily pain intensity on days 24-28 of each treatment phase, obtained from the patient diaries. The two slopes will be compared using t-test. Significant difference between slopes will indicate that baseline MPT correlates with pregabalin response (vs. placebo response) in painful CIPN, regardless of differences in average pain response between pregabalin and placebo.

As secondary analyses, we will compare mean absolute pain reduction with pregabalin to absolute pain reduction to placebo (both for average daily pain and maximum daily pain), using paired t-test, given normal data distribution. If normal distribution is not obtained, we will use Wilcoxon signed ranked test. In addition, we will perform Fisher exact test to compare the proportion of patients with 50% or more reduction in average pain intensity from baseline with pregabalin vs. placebo. Number needed to treat (NNT) will be calculated from this proportion of responders to pregabalin and placebo. These secondary analyses are aimed at detecting group differences in response to pregabalin vs. placebo.

In exploratory analysis, we will examine the correlations between the various demographical and QST variables (WDT, CDT, HPT, CPT, WSI, TS, CPM) and pain reduction with pregabalin vs placebo, for generating hypotheses for additional predictors of response to pregabalin in CIPN. We will also perform exploratory multiple regression analysis to evaluate how various QST factors perform in combination as treatment response predictors.

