2.4.8 Sample Size

The sample size calculation was performed for detecting a significant difference between correlations on % pain reduction vs. MPT slopes of pregabalin and placebo in linear bivariate regression. Assuming slope and SD data based on our preliminary results of MPT vs. response with another drug, lidocaine (Haroutiunian, Nikolajsen et al. 2013); to detect 0.3 (SD=0.5) difference in correlation coefficients between the two slopes, with 85% power and alpha=0.05, 27 participant are required in this cross-over design. We will aim to recruit 35 patients to account for possible 20% dropout rate.

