2.4.9. Dealing with missing data

If less than 10% data on primary outcomes are missing, we will perform our primary analysis per protocol, and perform sensitivity analysis using intent to treat (ITT) approach, where missing pain intensity data will be imputed using last observation carried forward (LOCF) method. If more than 10% primary outcomes data are missing, we will use mixed-effects model imputation method [full information maximum likelihood (Little, D'Agostino et al. 2012)], which considers the reasons for missingness, and is more appropriate for reducing bias.

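### Does the slope comparison need a stated scale for baseline MPT, and a stated score when 512 mN is not painful, to be sound?

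*Combined protocol and SAP*

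**What the plan says.** Section 2.4.7 makes the primary outcome the "comparison of slopes of the two correlations: baseline MPT vs % pain reduction with pregabalin, and baseline MPT vs % pain reduction with placebo", with the two slopes compared by a t-test. MPT is the only predictor.

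Section 2.4.6 says how MPT is obtained. The probes are "exerting pressure of 8, 16, 32, 64, 128, 256 and 512 mN". Starting at 8 mN, "stimuli increase in intensity until the sensation induced by increased pressure can be described as" painful. The force of that probe is the value for the series, and MPT is the mean of three series. The same section asks for a geometric average for mechanical detection threshold and for wind-up, but not for MPT.

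Section 2.4.8 sizes the trial for a comparison that it describes as "pain reduction vs. MPT slopes of pregabalin and placebo in linear bivariate regression". The planning values were borrowed from earlier work by the investigators, and the section introduces them with the words "Assuming slope and SD data based on our preliminary results of MPT vs. response with another drug, lidocaine". It gives a difference of 0.3 with SD 0.5, 85% power, alpha 0.05 and 27 participants, with 35 recruited to allow for 20% dropout. The scale of the planning slopes is not given. In section 2.4.9, "missing pain intensity data will be imputed using last observation carried forward (LOCF) method"; nothing there concerns MPT.

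**The concern.** Two things are unwritten: the scale on which MPT enters the regression, and the value recorded when a series ends at 512 mN without pain.

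The first looks serious because the probe forces double. Equal steps on log2 are very unequal steps in mN, so a few patients with high thresholds can dominate a slope fitted in mN. The hypothesis, however, is about low thresholds.

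The second looks like an oversight because neighbouring tests carry limits or a fallback. For thermal testing, "Cut-off temperatures are 0°C and 50°C". For detection threshold there is an instruction that begins "In case the first von Frey filament with an intensity of 16mN is not detected". Painless series at 512 mN are also foreseeable, since section 2.1 describes nerve fibre degeneration and testing is on the foot.

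If these were truly open choices, an analyst could settle them after seeing the results, and the single primary test could turn on them.

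**Working it through.** **1. The plan's own figure.** The standardised difference is 0.3/0.5 = 0.6. A paired t-test with n = 27 and two-sided alpha 0.05 has noncentrality 0.6 × √27 = 3.12 and power 85.1%, so the stated 27 reproduces. For dropout, 27/0.8 = 33.75, or 34, which 35 covers; 35 × 0.8 = 28 completers. No scale of MPT enters this calculation, so the open point does not affect N.

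**2. What the text implies about scale.** MPT is recorded as a force, in mN, and averaged. Where the authors want a log-type summary (detection threshold, wind-up), they say so. Sections 2.4.7 and 2.4.8 then use MPT in a linear regression with no transformation. A variable defined in mN and entered untransformed is in mN.

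**3. What the neighbouring tests specify.** The thermal cut-offs are safety limits; the section does not say what is recorded when one is reached. The filament instruction concerns where to start when 16 mN is not felt, not what to record if no filament is felt. End-of-range scoring is therefore left to laboratory routine for every test, not for MPT alone.

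**4. Why scale has some effect.** Put one patient at each of the seven levels.
- In mN the mean is 1016/7 = 145.1 and the sum of squares is 349,504 − 1016²/7 = 202,039. The 512 mN level contributes (512 − 145.1)² = 134,584, or 67%.
- On log2 the values are 3 to 9, the sum of squares is 28, and the top level contributes 9/28 = 32%.
- The two scales correlate at 0.88.

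**5. How often scale changes the verdict.** All inputs here are assumptions, because the documents give no MPT distribution.
- The within-patient difference in % pain reduction is regressed on MPT; its slope equals the difference between the two slopes.
- There are 28 patients, and the true correlation is 0.54 (85% power at 27).
- Between-patient SD is 1.2–2.0 doublings and within-patient SD 0.5 doubling, with three readings rounded up to the next probe and the ceiling scored 512.
- Each setting has 20,000 trials. The table gives the share in which exactly one scale reaches p < 0.05.

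| MPT centre | Response linear in log2 | Response linear in mN |
|---|---|---|
| 32 mN | 14–18% | 12–18% |
| 64 mN | 12–13% | 14–17% |
| 128 mN | 8–10% | 12–14% |
| 256 mN | 6–8% | 8–11% |

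The scales therefore agree in 82–94% of trials. With 35 patients, disagreement falls to 5–14% and 7–16% for the two response shapes. A second simulation (SD 1.5 doublings, series SD 0.4, centres 64–256 mN) gives 6–14% at 27 patients and 4–10% at 35. When the scales disagree, the non-significant p-value is below 0.15 in about 75–98% of cases, and the two never gave significant slopes of opposite sign.

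**6. Whether one scale is better.** If response is linear in mN, log2 loses about 5–14 points of power. If response is linear in log2, mN loses about 2–14 points at centres 32–128 mN and none at 256. The cost is similar either way, and nothing in the documents shows which shape holds.

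**7. Error with no effect.** Each fit alone rejects in 4.6–5.2% of null trials. In the second simulation the two scales disagree in 3–4% of null trials.

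**8. The ceiling.** The expected number of patients with at least one painless series at 512 mN is 0.6–2.9 of 28 (centre 64 mN) or 2.9–6.1 (centre 128). With all three series painless it is 0.1–1.3 or 0.7–3.3. For log2 MPT with a log-linear response, scoring 512 gives power of 83–84% (centre 64) and 82–83% (centre 128). Averaging only the painful readings gives 76–83% and 65–77%. The natural score is also the one that preserves power.

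**The case for a change.** The strongest case is that there is one primary test with one predictor, so any freedom in that predictor matters. The span from 8 to 64 mN is half the doublings (3 of 6) but only 56/504 = 11% of the mN range, so in mN the low-threshold patients named in the hypothesis are bunched together. With a weaker true correlation of 0.4, the scales disagree in 8–20% of trials.

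Ceiling rules can matter as much. Scoring 512 against averaging only the painful readings changes the verdict in 1–24% of trials. On raw mN, 512 against 1024 changes it in 4–19%, and 512 against exclusion in 13–32%. Under no effect, reporting the better of two scales gives 6.1–7.4% error, and the best of six scale-and-ceiling combinations gives 10–12%.

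What stands is that neither point is written down, and that in a minority of plausible datasets the choice would move p across 0.05.

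The rest carries less weight. The inflated error rates require an analyst to try several versions and report the most favourable, whereas the plan describes one test on one defined variable. The large ceiling effects come from setting the obvious score against rules the documents nowhere suggest. In the second simulation, response was also generated from the 512-scored value, which counts against the alternatives by construction. The bunching of low thresholds is a reason to look at log2 as well, but it does not show mN to be wrong.

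**Conclusion.** No change to the plan follows. This is missing detail that an analyst fills sensibly: MPT in mN as section 2.4.6 defines it, and 512 mN for a series that ends without pain. MPT is measured before treatment, so a fixed scoring convention cannot depend on response, and the test keeps its 5% level on either scale. The required 27 and the planned 35 are unaffected. Prescribing log2 instead would bring no dependable gain, because each scale loses a similar amount of power if the other describes the response.

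The residual sensitivity is disagreement on significance in roughly 6–18% of trials with a true effect at 28 patients and planned power. It is less at the 35 evaluable patients named in the synopsis and in sections 2.3 and 2.4.1, and the disagreements mostly straddle 0.05. Section 2.4.1 calls the trial a pilot, and that is tolerable there.

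These percentages rest on assumed MPT centres, spreads and response shapes, and on regressing the within-patient difference on MPT, which section 2.4.7 does not spell out. The conclusion on the scale rests mainly on the wording of section 2.4.6 and would not change within the ranges shown.

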2.3.1 Inclusion Criteria

Inclusion criteria:

1. Age >18
2. Distal symmetric pain distribution (both feet, with or without pain in hands).
3. Pain appeared during or up to 12 weeks after treatment with oxaliplatin, paclitaxel, docetaxel or any combination of these.
4. Score of 4 or more on DN4 neuropathic pain questionnaire (Bouhassira, Attal et al. 2005).
5. Pain duration > 2 months.
6. Patient report of average daily pain intensity >3 on 0-10 Numerical Rating Scale (NRS) in the past week.
7. Women of childbearing potential and men must agree to use adequate contraception (hormonal or barrier method of birth control, abstinence) prior to study entry and for the duration of study participation. Should a woman become pregnant or suspect she is pregnant while participating in this study, she must inform her treating physician immediately.
8. Able and willing to sign an IRB-approved written informed consent.

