2.4.2 Pre-Study Period

At the screening visit, after obtaining signed informed consent, we will collect patient demographic data including details on cancer type and status, chemotherapy regimen(s) and cumulative doses, history of chronic pain, concomitant diseases and medication, and duration of painful CIPN. A blood sample for CMP will be obtained for determining serum creatinine concentration and liver transaminases (ALT and AST). If subject's lab tests results are available within the past 30 days, we will utilize these without the need of obtaining new renal and hepatic function tests. In addition, the patients will complete the following questionnaires: Brief Pain Inventory (BPI), Neuropathic Pain Symptom Inventory (NPSI), and Depression Anxiety and Positive Outlook Scale (DAPOS). Average and maximum daily pain intensity in the past week will be recorded as baseline pain intensity measure.

The subjects' extremities will be mapped for spontaneous pain, and response to the following sensory stimulation: cold (20°C Thermal Roller, Somedic), warm (40°C Thermal Roller, Somedic), pinprick (# 5.88 Semmes-Weinstein monofilament, 60mN target force, North Coast) and brush (SenseLab 0.5 brush, Somedic) (Finnerup, Sorensen et al. 2007). The probability of neuropathic pain will be graded as possible, probable, or definite according to Treede et al. criteria (Treede, Jensen et al. 2008). The results of sensory mapping will provide the information for the criterion on presence of any objectively tested positive or negative neurological signs in the painful territory. Photographs of the mapped extremities will be taken (in a way not to include any part of the subjects' face or other identifying information), for accurate reproduction of areas of sensory disturbance.

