Patients will complete an electronic diary with daily report of their average and maximum daily pain intensity, recorded every evening before bedtime. The percentage of pain reduction for primary outcome will be assessed from the difference between baseline average pain intensity and the average pain intensity of last 5 days of treatment (day 24-28), on 0-10 NRS.

Secondary efficacy outcomes will include: 1) The difference between baseline maximum pain intensity and the maximum pain intensity of the last 5 days of treatment, on 0-10 NRS; 2) The proportion of patients achieving 50% or more pain relief with pregabalin vs. placebo treatment; 3) Difference in Pain Severity and Pain Interference scales of the BPI, assessed at baseline and day 28 of treatment. The daily use of rescue analgesia (oral acetaminophen) will also be recorded.

Table 1. Data assessment schedule

Required Assessments	Screening and Enrollment Baseline Visit	Week 1a	Week 2a	Week 3a	Week 4a	End of Treatment A (Day 28 +/- 2)	Wash-out	Study crossover visit	Week 1b	Week 2b	Week 3b	Week 4b	End of Study Visit (Day 30 +/- 3)
Study visits	Visit1 (a/b)*					Visit2		Visit3					Visit 4
Informed consent	✓												
Pregnancy (urine Hbhcg) test for women	✓												
Comprehensive Metabolic Panel (CMP) blood test**	✓					✓							✓
Inclusion/exclusion criteria	✓												
Randomization	✓												
Demographic data collection	✓												
Sensory Mapping	✓					✓		✓					✓
BPI questionnaire	✓				✓			✓				✓	
NPSI questionnaire	✓				✓			✓				✓	
DAPOS questionnaire	✓				✓			✓				✓	
SPI questionnaire	✓				✓			✓				✓	
QST	✓							✓					
CPM	✓							✓					
Dispense study drug	✓							✓					
Pain intensity 0-10 NRS	✓	daily	daily	daily	daily			✓	daily	daily	daily	daily	✓
Adverse Event assessment		daily	daily	daily	daily				daily	daily	daily	daily	✓
Telephone communication		weekly	weekly	weekly	weekly				weekly	weekly	weekly	weekly	
Blinding questionnaire***		✓											
Pill count								✓					✓
Blood sample (PK)						✓							✓
Skin biopsy (optional)													✓

*Visit 1 may be conducted over 2 visits to complete all assessments if required for subject tolerability or convenience

** A blood sample for CMP will not be obtained if recent (<30 days) results are available.

*** Blinding questionnaire to be administered via EMA device on Day 5 of study drug treatment

Subject Blinding Perception

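### The primary slope comparison leaves out baseline pain, the outcome's denominator; an adjusted slope difference should be pre-specified beside it

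*Combined protocol and SAP*

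**What the plan says.** Section 2.4.7 of the combined protocol and SAP defines the primary analysis as two regressions, "baseline MPT vs % pain reduction with pregabalin, and baseline MPT vs % pain reduction with placebo", and adds "The two slopes will be compared using t-test". Section 2.4.8 sizes the trial for "MPT slopes of pregabalin and placebo in linear bivariate regression", which confirms a single predictor.

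The outcome is a percentage change: "Percent pain reduction will be assessed from the difference in average pain intensity at baseline and the average daily pain intensity on days 24-28". Section 2.4.3 says the same under Clinical Efficacy. Baseline pain is therefore the denominator. It is recorded in every patient (2.4.2: "Average and maximum daily pain intensity in the past week will be recorded as baseline pain intensity measure"), and eligibility lets it run from just above 3 up to 10 (2.3.1: "Patient report of average daily pain intensity >3 on 0-10 Numerical Rating Scale (NRS) in the past week").

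No planned analysis includes baseline pain as a predictor. The exploratory correlations in 2.4.7 name demographic and QST variables, and the exploratory multiple regression names QST factors. Absolute pain reduction is compared only as a group mean, never against MPT. The documents do not discuss a link between MPT and baseline pain.

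**The concern.** The cross-over removes baseline pain as a main effect but not as a modifier of the treatment difference. When one baseline serves both periods, it cancels from the numerator of the within-patient difference and stays as the divisor. A benefit of the same size in NRS points then counts for more, in percent, in a patient with mild baseline pain than in one with severe pain.

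MPT is an observed trait. If it goes with baseline pain, the denominator can produce a slope on MPT, or hide one. Section 2.4.7 would read a significant slope difference as showing that MPT relates to pregabalin response. The trial sets out to find somatosensory predictors, so telling MPT apart from severity matters for how the result is read. As planned, no analysis would do so.

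**Working it through.** **Inputs from the documents.** One predictor, and an outcome in percent of baseline (2.4.7, 2.4.8); baseline NRS above 3 and up to 10 (2.3.1); "to detect 0.3 (SD=0.5) difference in correlation coefficients between the two slopes, with 85% power and alpha=0.05", 27 participants required, 35 recruited for 20% dropout (2.4.8).

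**The plan's own figure.** A paired t-test on 0.3/0.5 = 0.6, two-sided alpha 0.05, noncentral t, needs N = 27 (power 85.1%). The stated 27 reproduces and is not in question here. Of 35 recruited, 35 × 0.8 = 28 would remain.

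**Algebra.** With one baseline B per patient:

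- % reduction on pregabalin = 100(B − Y_pregabalin)/B, and likewise for placebo.
- Within-patient difference = 100(Y_placebo − Y_pregabalin)/B.
- A 2-point benefit is 100 × 2/4 = 50% at B = 4 and 100 × 2/8 = 25% at B = 8.

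**Simulation assumptions (none of these values is in the documents).** Baseline NRS has mean 5.5 and SD 1.6, limited to the eligible range. MPT is standardised. r is the correlation of MPT with baseline pain; r < 0 means that sensitive (low-MPT) patients have more pain. Benefit is additive in NRS points. The within-patient difference is regressed on MPT, without and with baseline pain.

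Results for N = 27, mean benefit 2 points, shared patient SD 1, residual SD 1 per period, 20,000 runs. Slopes are in percentage points per SD of MPT; the hypothesis predicts a negative slope. Each pair is unadjusted / adjusted.

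| r | No MPT effect: unadjusted slope | No MPT effect: rejection | True MPT effect: slope | True MPT effect: power |
|---|---|---|---|---|
| 0 | 0.0 | 4.9% / 4.9% | −10.9 / −10.9 | 51% / 52% |
| −0.3 | +1.9 | 6.3% / 5.2% | −9.0 / −11.0 | 37% / 48% |
| −0.5 | +3.3 | 9.0% / 5.0% | −7.7 / −11.0 | 28% / 42% |
| +0.3 | not run | not run | −12.6 / −10.8 | 62% / 48% |
| +0.5 | not run | not run | −13.9 / −10.7 | 68% / 40% |

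These powers depend on the assumed effect and are not comparable with the plan's 85%.

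**Size of the distortion, r = −0.3 / −0.5.**

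- Mean benefit 2 points (table): 1 − 9.0/11.0 = 18%; 1 − 7.7/11.0 = 30% too small.
- Mean benefit 1 point (same settings): 1 − 10.5/11.6 = 9-10%; 1 − 9.8/11.7 = 16-17%.
- Mean benefit 1.5 points plus 0.7 per SD lower MPT, n = 28, period SD 1.2: 11-14% and 20-25% across separate sets of runs. Power is about 37-39% / 29-30% unadjusted and 43-46% / 37-40% adjusted.
- False positives with no MPT effect and a constant 2-point benefit: about 6-7% and 9-10% across runs; with 1 point (N = 27), 5.6% and 6.4%.

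**Where the distortion disappears.** At r = 0, or with no average drug effect, unadjusted rejection without an MPT effect is 4.9-5.3%. If benefit is proportional to baseline pain, the unadjusted slope without an MPT effect is −0.1 to −0.5 and rejection 4.9-5.1% (r = −0.5).

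**What adjustment costs.** Under proportional benefit, power falls from 48-50% to 44-45% at r = −0.3 and from 46-49% to 37-38% at r = −0.5. If adjustment reduces no variance, the N for equal power is about 27/(1 − r²): 27/0.91 = 30 at 0.3 and 27/0.75 = 36 at 0.5. The latter exceeds the 35 to be recruited.

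**The case against.** The strongest reply is that section 2.2 sets the objective as the correlation of MPT with percent pain reduction, pregabalin against placebo. That is a marginal prediction question, and a predictor that works partly through its link with severity still predicts. Adjusting for baseline pain asks something else: whether MPT adds information beyond severity. This stands, and it is why the unadjusted comparison should stay primary.

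The distortion also needs two things that the documents do not supply: a correlation between MPT and baseline pain, for which neither size nor sign is given, and a benefit that is not proportional to baseline. A percentage outcome fits naturally with proportional benefit. This too stands; it limits the size of the point but does not remove it, because nobody can know beforehand which case holds.

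A reader might infer that the planned test is invalid, or that the adjusted model must replace it. The documents do not support that. The adjusted model gains power in some cases and loses it in others, and section 2.4.1 calls the trial a pilot. A reader might also infer a bias towards the hypothesis. If sensitive patients have more pain, the spurious slope is positive and works against it; false support needs the opposite correlation. Nor are the two explanations inseparable in principle: the data are collected, and only the analysis is missing.

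Finally, the algebra assumes one baseline per patient. Table 1 also schedules an NRS rating at the crossover visit, and 2.4.7 does not say which value serves period 2.

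**Conclusion.** The point holds as a gap in the planned analyses, not as an error in the primary test. Baseline pain is the outcome's denominator and appears in no planned model, so a slope difference on MPT could partly reflect baseline severity, or be masked by it, without the trial being able to show this.

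Under an assumed |r| of 0.3-0.5 and additive benefit, the slope difference is about 11-25% too small when low-MPT patients have more pain (10-30% as the mean benefit goes from 1 to 2 points), and too large in the opposite case. With no MPT effect and a constant 2-point benefit, the false-positive rate is about 6-10% instead of 5%. The distortion is absent at r = 0 and negligible with proportional benefit. All these sizes depend on assumed values.

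**What to change.** In section 2.4.7:

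- Keep the unadjusted slope difference as the primary test.
- Pre-specify beside it, before unblinding, an analysis that adds baseline average pain and its interaction with treatment. With one baseline per patient, this is the within-patient difference in percent reduction regressed on MPT and baseline pain. A baseline main effect common to both treatments is not enough: with complete pairs it leaves the slope difference unchanged.
- Let the conclusion that MPT itself predicts pregabalin response rest on both analyses agreeing, and say what agreement means. Same direction and similar size, with confidence intervals, would suit better than a second significance test, given the adjusted model's limited power.
- State whether period 2 uses the screening or the Visit 3 pain rating as baseline. If baselines differ by period, the single-covariate within-patient form no longer applies, and the two-period model with the interaction is needed.

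The cost is a few sentences, one extra model and one degree of freedom in the within-patient form; no new data are needed. The downside is that the adjusted analysis has about 5-10 points less power at |r| 0.3-0.5 if benefit is proportional to baseline, which is why it should accompany the primary test and not replace it.
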